Kansas City Cardiomyopathy Questionnaire (KCCQ)(Appendix): is a 23 item instrument validated in stable and decompensated HF patients with preserved or reduced ejection fraction. The questionnaire takes 4-6 minutes to complete, and reflects disease-specific health status over the prior two weeks. The domains of KCCQ are physical limitation, symptoms, self-efficacy, social limitation, and quality of life. The domains of the KCCQ have a high internal consistency with a Cronbach's alpha of 0.95 for the Overall Summary Score and  $\geq 0.62$  for all individual scales. The KCCQ has a significantly higher responsiveness to changes in health status than the Minnesota Living with Heart Failure Questionnaire and the SF-36. The overall summary score is 0-100 where higher score is better. The minimal clinically important change in survey score is 5 points, with a 10- and 20-point change reflecting moderate and large clinical changes, respectively. In the Eplerenone Post-AMI Heart Failure Efficacy and Survival Trial (EPHESUS), each 5-point decline in KCCQ Overall Summary Score on serial assessments was associated with a hazard ratio of 1.11 (95% CI, 1.05-1.17) for subsequent cardiovascular death or hospitalization. Preliminary data from Phoenix VA found a median Summary Score of  $52.4 \pm 27.8$  (n =32) in HF-SMA participants indicating fair/poor health status.

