#### Other data collection tools:

Aside from demographics (age, gender, housing situation, social support, marital status, service connection, employment, education), we will also collect data about depression symptoms and patient's perception of care coordination for subgroup analysis and risk adjustment.

**Depression symptoms – The Patient Health Questionnaire-8 (PHQ-8, appendix)** is a 8-item well validated self-administered instrument that is a reliable measure of depression severity and depression symptom burden and is responsive to treatment outcomes over time. Scores can range from 0 to 24, with a higher score indicating a greater burden of depressive symptoms. PHQ-8 scores of 5, 10, and 20 represented mild, moderate, and severe depression, respectively. Internal reliability estimates range from 0.86 to 0.89 using Cronbach's alpha. Two day test-retest reliability is estimated to be 0.84 with nearly identical mean total scores. The advantages of the PHQ-8 include the following: 1) It is self-administered; 2) It contains only 8 questions that help identify patients with clinically meaningful symptoms of depression; 3) Can be reasonably administered in 5-10 minutes; and 4) Can be scored in 1-2 minutes. For safety guards in place regarding suicidal ideation, please refer to Human Subjects section.

**Perceived patient-centeredness and coordinated care (PACIC survey) (Appendix):** The PACIC is a well-validated 20-item questionnaire that has 5 subscales: Patient Activation, Delivery System Design/Decision Support, Goal Setting, Problem-solving/Contextual Counseling, Care Coordination; with the various scales, as well as the overall score, to be both internally consistent and moderately stable during test-retest. This tool assesses the health care system from the patient's perspective (patient centeredness). The questions are general enough that we can ask the patient to answer in the context of their heart disease care.

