**Medical co-morbidities and cardiac history:** based on the Charlson Co-morbidity index, this data will be collected through chart abstraction by our research assistants at baseline and confirm it with patient and caregiver. The Charlson Co-morbidity index is a weighted index that takes into account the number and the seriousness of comorbid disease. The index is well validated for its ability to predict risk of death from co-morbidities at 1-year and 10-year follow-up periods. We will also obtain cardiac testing data including echocardiography, cardiac catheterization, and stress test data through review of medical records. Non-VA sources will be contacted if indicated to track non-VA care (Table 1 of data collection below)

Table 1. Timeline of Data Collection	Baseline	90 days	180 days	Data Source
Charlson Comorbidity Index	X			Patient, family and chart
Caregivers / Demographics	X			Patient, family and chart
Echocardiography, cardiac testings	X			Patient and chart
KCCQ, EQ-5D	X	X	X	Patient
HF Self-care Index, PACIC, PHQ-8, BNP	X	X	X	Patient
Patient (± caregiver) satisfaction	Ongoing			Interview
Provider perception	Ongoing			Interview
Hospital admission or death	Ongoing			Patient, family and chart
HF clinics / programs	Ongoing			Patient, family and chart
Outpatient physician and ER visits	Ongoing			Patient, family and chart

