Aim 2: To compare between the intervention versus usual care arms in hospitalization or death at 90 and 180 days after the randomization. For this analysis Cox proportional hazards model will be utilized where the event is a composite outcome that represents either hospitalization or death. Any patient who does not experience the event by 180 days will be denoted as censored. The main exposure is treatment group and other covariates include patient demographic and comorbidity information as described above. We will examine the differences in outcome at both 90 and 180 days. The appropriateness of the proportional hazards assumption will be examined and any violation of the assumption will be addressed. The appropriateness of the functional forms of each covariate will be assessed through residual analysis.

Aim 3: To compare between the intervention versus usual care arms in the change from baseline in patient's (a) HF Self Care index and (b) BNP levels, we will use the same linear mixed-effects modeling approach as described in Aim 1.

Subgroup and Sensitivity Analyses: In order to understand potential heterogeneity of treatment effects, stratified analyses will be conducted by our randomization stratifiers such as co-interventions or not, ejection fraction ( $\geq 40\%$  &  $< 40\%$ ), and hospitalizations in the previous 6 months ( $> 2$  &  $\leq 2$ ). Given that baseline KCCQ scores, HF self-care behavior, comorbidity burden, depression symptoms and caregiver support could potentially change the outcome of HF, we will conduct test for multiplicative interaction between the condition of interest (e.g. depression with PHQ-8  $\geq 10$  vs.  $< 10$ ) and the study arm allocation (intervention vs. usual care arm) on the patient outcomes of interest described in Aims 1 and 2. *If any these interaction terms are significant at an alpha level of 0.05 or less*, subgroup analyses will be conducted (e.g. number of comorbidities below and above the median, baseline KCCQ scores above and below the median, and by presence or absence of significant depression symptoms or caregiver support) depending on the feasibility by sample size. Sensitivity analyses will be performed by study site to determine the impact of setting in our study findings and potential variation of findings.

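### The one interaction test the plan illustrates cuts the PHQ-8 score at 10, the coding of the other scored modifiers is not stated, and the follow-up subgroups use sample medians

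*Combined protocol and SAP*

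**What the plan says.** The relevant text is in section 9, Subgroup and Sensitivity Analyses. It names baseline KCCQ, self-care behavior, comorbidity burden, depression symptoms and caregiver support as factors that "could potentially change the outcome of HF". It then sets out two steps.

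- **Step 1, the test.** "we will conduct test for multiplicative interaction between the condition of interest (e.g. depression with PHQ-8" at 10 or more against below 10), with study arm as the other term. This is the only example of how a modifier is coded in a test.
- **Step 2, the subgroups.** These start only on a condition, "If any these interaction terms are significant at an alpha level of 0.05 or less". The examples include "number of comorbidities below and above the median, baseline KCCQ scores above and below the median", and presence or absence of significant depression symptoms or of caregiver support. They are also limited by "depending on the feasibility by sample size".

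The modifiers are collected as scores. For KCCQ (section 8, Aim 1), "The overall summary score is 0-100 where higher score is better". For PHQ-8 (Other data collection tools), "Scores can range from 0 to 24, with a higher score indicating a greater burden of depressive symptoms". Each self-care scale runs from 0 to 100 (section 8, Aim 3). For comorbidity, "The Charlson Co-morbidity index is a weighted index that takes into account the number and the seriousness of comorbid disease".

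**The concern.** Cutting a score treats everyone on one side of the cut as alike, so an interaction test on the cut score usually has less power than one on the score itself. Here the test is also a gate: if it misses 0.05, the step 2 subgroup analyses for that modifier are not run. Learning who benefits is a declared purpose of the trial. The Specific Aims ask which groups the diabetes results carry over to, Innovation hopes to find favorable subgroups even if the overall result is not significant, and section 11 wants to know which patients to target.

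The median splits raise a separate problem of meaning. A sample median moves with case mix, so a finding for patients above the median gives another hospital no score to apply. And if step 1 is run on the score while step 2 reports halves, the subgroups shown are not what was tested.

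**Working it through.** **Inputs from the documents** (section 9, Sample Size and Power Considerations, and Table 2): SD 15, 158 patients per arm, two-sided 0.05, and power 0.84 for a 5-point KCCQ difference. No power is given for any interaction test, and no modifier distribution is given.

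**1. The plan's own figure.** SE of the difference = 15 × √(2/158) = 1.69. Power for 5 points = Φ(5/1.69 − 1.96) = 0.84. Differences of 4.5, 5.5 and 6 points give 0.760, 0.903 and 0.945, against 0.76, 0.90 and 0.95 in Table 2. Aim 1 reproduces.

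**2. Starting point for interactions.** For two subgroups of equal size, the SE of the difference between their treatment effects is 2 × 1.69 = 3.38. A 5-point difference in effect then has power Φ(5/3.38 − 1.96) ≈ 0.32. There is little power to give away.

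**3. Information kept after a cut.** Assume the treatment effect is linear in the score. Randomization makes arm independent of the modifier, so the share of interaction information kept is the squared correlation between the score and its split. For a normal score with a share q above the cut point c, this is φ(c)²/[q(1 − q)]:

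| Share above cut | Kept | Lost |
|---|---|---|
| 50% (median) | 0.637 | 36% |
| 30% | 0.576 | 42% |
| 25% | 0.539 | 46% |
| 20% | 0.490 | 51% |
| 10% | 0.342 | 66% |

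**4. Other assumed shapes.**
- Uniform, cut at the median: 25% lost.
- PHQ-like score on 0-24 cut at 10: 34% lost (normal with mean 8 and SD 5.5, rounded and truncated) or 32% lost (right-skewed, mean about 7), so about 33%.
- KCCQ-like score on 0-100, using the Phoenix pilot figures of 52.4 and 27.8 as mean and SD, cut at the median: 32% lost.
- Poisson-like counts (means 2 to 4) cut near the median: 33% to 39% lost.
- Exponential, cut at the median: 52% lost.

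**5. Effect on power.** Take a hypothetical test with 0.80 power on the continuous score, so that z = 1.96 + 0.84 = 2.80. Power after cutting = Φ(2.80 × √kept − 1.96).
- Normal score at the median: Φ(2.80 × 0.798 − 1.96) = 0.61.
- Normal score with 30% above the cut: 0.57.
- Normal score with 25% above the cut: 0.54.

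A simulation with 316 patients, SD 15 and 5,000 runs per cut gave 0.80 (continuous) against 0.60 (median split), and 0.79 against 0.55 with 30% above the cut.

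**6. Movement of the median.** Section 8 reports a Phoenix pilot KCCQ median of 52.4, while the sample size section assumes a baseline of 63 from preliminary studies. The gap is 63 − 52.4 = 10.6 points, about twice the 5-point minimal important change. The two figures may not be the same statistic, but they show how far a sample-based cut could shift.

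**The case against.** A reader might infer that all the scored modifiers are split before they are tested, so that the median splits themselves weaken the interaction tests. The documents do not support that. The median splits are examples within step 2, which begins after an interaction has been declared significant, and a cut made then cannot cost that test any power. For KCCQ, self-care and comorbidity the plan is silent on the coding in step 1. No median split of PHQ-8 and no cut of the self-care index appears anywhere.

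Three further points stand on the other side. A PHQ-8 of 10 is the instrument's moderate-depression threshold (Other data collection tools), so the complaint about sample dependence does not reach it; that complaint applies only to the KCCQ and comorbidity medians. Section 9 also plans residual checks of functional form, which suggests that continuous terms are expected in the models, although it does not settle the interaction terms. Finally, who benefits is a declared purpose but is not among Aims 1 to 4, and the subgroup work is made conditional on sample size.

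The objection therefore removes the claim of a demonstrated loss for every modifier. It leaves the PHQ-8 test, which is dichotomized, and the missing specification for the rest.

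**Conclusion.** The point holds in limited form, as a minor improvement. The depression interaction test uses a cut score, and the plan leaves open how the other scores are tested. The follow-up subgroups for KCCQ and comorbidity rest on sample medians that cannot be carried elsewhere.

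The loss is about a third of the information for a PHQ-like score cut at 10. It ranges from roughly 25% to 52% across the median-cut and PHQ-like shapes tried, and is larger for very uneven cuts. These figures assume a linear effect and assumed distributions; the fall from 0.80 to 0.61 also assumes a normal score and a hypothetical starting power. A reader might take a loss of a third to a half as established for this trial, but without the modifier distributions it is not. If the true effect were a step at 10, the cut would not lose power in this way.

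**What to change.** Amend the subgroup paragraph of section 9 to state three things:

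- Each scored modifier (PHQ-8, baseline KCCQ, self-care index, Charlson index) enters the treatment-by-modifier test as a continuous term, with a spline as a check on linearity.
- The estimated SMA effect, with its confidence interval, is reported across the observed score range.
- PHQ-8 of 10 and any median cuts are used only for descriptive display.

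The cost is SAP wording and a plot for each modifier reported. The data are already collected and no visits or patients are added. The downside is that a linear term can miss a threshold effect, which the spline check is there to show.

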Mediating Factor Analyses: In order to understand the mechanisms by which HF-SMA improves health status and hospitalization or death, we will explore potential mechanisms from the process measures such as HF-self-care index and perceived care coordination (PACIC survey). In order to prove mediation, four conditions must be met: (1) correlation between the change in treatment variable (HF-SMA or not) with the change in mediator (change in process measure, e.g. HF self-care index); (2) variation in the mediator must be correlated with variation in the outcomes (e.g. KCCQ); (3) controlling for the mediator substantially reduces or eliminates the relationship between the treatment and outcomes; and (4) the treatment variable must temporally precede the mediator, which is inherent in our study because enrolled patients will be treatment naive. We will

compare multivariate regression model specifications that serially exclude and include the potential mediators and the treatment variable.

Exploratory Analysis on Study Generalizability and External Validity: We will compare the baseline characteristics and study outcomes of enrolled patients with those in the Registry of Excluded patients to assess for potential differences in characteristics and outcomes. If there are significant differences in baseline characteristics, an “as treated” analysis will be performed to compare on the study outcomes while adjusting for differences in baseline characteristics between excluded patients and patients who received HF-SMA using the same approaches we described for Aims 1 and 2. Although we understand that the excluded patients may be fundamentally distinct from the study population, these analyses will help to make inferences on the potential effects of the intervention on untreated patients and explore the generalizability of our findings.

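### The mediation conditions order treatment before mediator but not mediator before outcome, so association without mediation could be reported as mechanism

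*Combined protocol and SAP*

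**What the plan says.** The Mediating Factor Analyses paragraph of section 9 names the HF self-care index and PACIC as candidate mediators of health status and of hospitalization or death. It opens its rule with "In order to prove mediation, four conditions must be met". In summary, the conditions are:

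1. treatment correlates with change in the mediator;
2. variation in the mediator correlates with variation in the outcome;
3. "controlling for the mediator substantially reduces or eliminates the relationship between the treatment and outcomes";
4. "the treatment variable must temporally precede the mediator", which the plan takes as given because patients have had no SMA treatment at enrolment.

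The method is to "compare multivariate regression model specifications that serially exclude and include the potential mediators and the treatment variable". No visit pairing, lag, landmark or time-varying mediator is given there or elsewhere.

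Table 1 (Timeline of Data Collection) puts the row "HF Self-care Index, PACIC, PHQ-8, BNP" at baseline, 90 and 180 days, the same three visits as KCCQ. For Aim 2, section 9 says that "the event is a composite outcome that represents either hospitalization or death", and section 8 has events captured from randomization onward. Section E plans a separate paper on what mediates the KCCQ change and any reduction in hospitalization or death.

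**The concern.** Mediation is a claim about sequence: treatment changes the mediator, which then changes the outcome. The background section states the theory in that order, with self-care improving first, then health status, then hospitalizations. The four conditions secure only the first link. Randomization makes condition 4 true whatever happens between mediator and outcome, so it screens out nothing at that link.

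Three alternatives could pass the rule:

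- **Reverse causation.** A patient who feels better may report better self-care at the same visit. The self-care index covers noticing symptom changes, and symptoms are a KCCQ domain.
- **A shared cause.** Depression or comorbidity, for example, could move both scores.
- **Events before measurement.** A patient who dies before the 90-day visit never has a post-baseline mediator value. A patient hospitalized before it has a value that the admission may have altered.

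At stake is the planned mediation paper, which could report a mechanism that the data do not show.

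**Working it through.** The plan gives no figure for the mediation analysis, so there is none to reproduce. The illustrations below borrow its other inputs.

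**Inputs from the documents**
- KCCQ difference b = 5, SD_Y = 15, 158 per arm (Sample Size and Power Considerations). Check: 5 / (15 × √(2/158)) = 2.96, and Φ(2.96 − 1.96) = 0.84, as in Table 2.
- Self-care index SD_M = 19.9 (Phoenix pilot, section 8). The same paragraph calls half an SD about 8 points, which implies SD_M ≈ 16.
- Event rate about 40% at 180 days (sample size paragraph).
- Visit windows 90 ± 30 and 180 ± 30 days (section 8).

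**Assumptions.** The mediator–KCCQ correlation within arm, r, is not in the documents; 0.2 to 0.5 is assumed. In the second case below, SMA is assumed to raise self-care by a = 8 points.

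**Apparent mediation with no effect of mediator on outcome.** Let a be the treatment effect on the mediator. Adjusting KCCQ for the mediator shrinks the treatment effect by a × r × SD_Y/SD_M.

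*Pure reverse causation.* If KCCQ alone drives self-care, then a = r × (SD_M/SD_Y) × b, so the shrinkage is r² × b:
- r = 0.2: 0.04, or 4%
- r = 0.5: 0.25, or 25%

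*SMA also raises self-care by 8 points, and the two scores are correlated within arm for other reasons:*
- r = 0.2: 8 × 0.2 × 15/19.9 = 1.21 points; 1.21/5 = 24%
- r = 0.5: 8 × 0.5 × 15/19.9 = 3.02 points; 3.02/5 = 60%
- with SD_M = 16 the range is 30% to 75%

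**How often the rule would be met.** This was simulated with 4,000 trials of 158 per arm, b = 5, SD_M = 16 and no mediator effect on KCCQ. *Met* means a significant total effect, a significant treatment effect on the mediator, a significant mediator coefficient, and at least 20% attenuation. The 20% cut-off is assumed, since the plan sets none.

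| r | Pure reverse causation | Shared cause, SMA adds 8 points |
|---|---|---|
| 0.3 | 7% | 82% |
| 0.5 | 31% | 84% |
| 0.7 | 53% | 85% |

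**Event timing.** With 40% events by day 180 and a constant hazard, the share of events before day t is (1 − 0.6^(t/180)) / 0.4.
- t = 60: (1 − 0.843)/0.4 = 39%
- t = 90: (1 − 0.775)/0.4 = 56%
- t = 120: (1 − 0.711)/0.4 = 72%

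With 40% in both arms, 316 × 0.40 ≈ 126 events are expected. About 126 × (1 − 0.564) ≈ 55 fall after day 90. For a visit at day 60 or day 120, about 77 or 35 would remain.

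**The case against.** The strongest reply is that the paragraph is silent on timing, not wrong about it. It says it will explore mechanisms and fixes no visit pairing. Table 1 supplies both 90- and 180-day values, so a lagged analysis is open under the present text. Mediation is in none of the four aims and is unpowered. This stands in part: a reader might infer that the plan commits to same-visit analysis, and it does not. But the paragraph also states the conditions as what it takes to prove mediation, and those conditions can be met without it.

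Three stronger inferences are tempting and should not be drawn.

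- **That 24–60% is what reverse causation alone produces.** Reverse causation alone gives r², or 4–25%, and at modest r it often fails condition 1. The larger range needs SMA also to raise self-care directly. The high simulated rates come from a shared cause, which time order alone does not cure.
- **That early readmissions push 72–79% of events before day 90.** This would place the 20–25% 30-day readmission rates in the first trial month. Those rates run from discharge. Enrolment may be up to 12 weeks after discharge, and the Providence pilot reports a mean delay of 41 ± 64 days from discharge to SMA attendance. The 40% input is also a post-hospitalization rate, but the plan itself adopts it for trial follow-up.
- **That the mediation paper would steer roll-out to the wrong SMA components.** The mediators are patient-level scores, not components. Section E assigns the implementation guide to the qualitative paper, and roll-out depends on proven effectiveness.

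**Conclusion.** The concern holds: the stated rule could be satisfied with no mediation, and the event part is the clearest case. Its size depends on a correlation the documents do not give. At r = 0.2 to 0.5, apparent mediation is 4–25% under pure reverse causation. It is 24–60% of a 5-point effect if SMA also raises self-care by 8 points (pilot SD 19.9) with no effect of self-care on KCCQ. Under a constant hazard and the plan's 40%, about 56% of events precede a day-90 mediator measurement, or 39–72% across the visit window.

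This is a secondary, exploratory analysis. The primary KCCQ comparison and the Aim 2 comparison between arms do not depend on it. It should still be corrected before analysis, because a separate paper will rest on it.

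**What to change.** - **Conditions.** Add that the mediator must precede the outcome, and replace the claim to prove mediation with a claim to assess it.
- **KCCQ.** Relate baseline-to-90-day mediator change to 180-day KCCQ, adjusting for arm, baseline mediator, baseline KCCQ, and baseline confounders already collected (PHQ-8, Charlson, BNP). The windows (60–120 and 150–210 days) do not overlap, so the order is assured. Report the model with and without 90-day KCCQ. Including it removes mediation already achieved by the 90-day visit, which matters because section 11 expects benefit to be greatest while sessions run. Leaving it out lets same-visit association carry forward.
- **Hospitalization or death.** Use a landmark at each patient's actual 90-day visit date, include only patients event-free then, and count later events to day 180. A fixed day-90 landmark could precede a mediator measured as late as day 120.

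The cost is SAP wording and analysis time; no new data are needed. The downsides should be stated in the SAP and the paper. About 55 of 126 expected events remain. The landmark set is selected after randomization, possibly differently by arm. Only mediation after the 90-day visit is estimated. Unmeasured shared causes remain possible.

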#### 9. Quantitative Analytic Plan:

Aim 1: To compare between the intervention versus usual care arms in the change from baseline in KCCQ (Primary outcome) and EQ5D (secondary outcome) at 90 and 180 days. The analysis will be performed from an intention to treat principle. First, descriptive statistics (mean, standard deviation, median, inter-quartile range, and frequency distribution) will be calculated to summarize, at baseline, patients' demographic and comorbidities including previous hospitalizations, cardiac history (heart function and coronary disease), medical and health service utilization information (including medication possession ratio, HF self-care index, BNP levels, enrollment into HF clinics / programs, visits with primary care and cardiologists), and the primary outcome of interest (KCCQ, overall score) according to randomized arms. Log-transformation of variables and outcomes of interest will be performed to approximate normality when appropriate. Linear mixed-effects (LME) model will be utilized for the analysis of this aim, where the response variable is KCCQ, fixed effects include treatment group, time (0 = baseline, 1 = at 90 days, 2 = 180 days), treatment group by time interaction, and other important demographic variables identified in the descriptive analysis, and random effects include site-specific random intercept, subject-specific random intercept (nested within site) and subject-specific random slope of time. This modeling approach has been shown to provide an unbiased and efficient estimate of the longitudinal treatment effect in a variety of situations, such as in the presence of missing data, imbalance of the primary outcome at baseline, and covariance heterogeneity between treatment groups. In this way, we could compare the intervention effects at 90 days and whether residual effects exist at 180 days. The random site effect is used to model the clustering effect of patients in the same study site and random subject effects are used to model the variability in the subject-specific trajectory and the correlation of repeated measures within subject. Residual analysis will be conducted to examine the appropriateness of the functional forms of each fixed effect, and Information criteria (AIC, BIC) will be used to choose the correlation structure.

Secondary: Same modeling technique will be used to study EQ5D as the outcome instead of KCCQ.

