Missing Data Issues: Since these are primary data collected as part of a clinical trial, we do not anticipate significant missing data. We will also record and report all reasons for dropout and missing data, and account for all patients in our reports as well as study publications. Overall, if the number of observations with missing values is small (<5%), we will conduct analyses by removing the variables with missing values. If the number of observations with missing values is many, we will compare characteristics between dropouts and those who had completed all the study visits. If it is determined that missing data is random, we will resort to methods that impute values, SAS Proc MI and MIANALYZE readily impute maximum likelihood estimates from incomplete data. If significant differences are found in the attrition rates across study arms, both ‘intention to treat’ and ‘as treated’ analyses will be performed to determine the extent to which the missing data may be biasing the results. For the ‘intention to treat’ analysis, we will generate actual random raw data values suitable for filling in gaps in an existing database. Typically, five to ten databases are created in this fashion. We will then analyze these data matrices using an appropriate statistical method, treating these databases as if they were based on complete case data. The results for these analyses are then combined into a single summary finding.

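### The as-treated comparison planned for unequal attrition is not a valid measure of missing-data bias in KCCQ, and the plan has no analysis for data that are not missing at random

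*Combined protocol and SAP*

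**What the plan says.** Section 9 (Quantitative Analytic Plan), Aim 1, states: "The analysis will be performed from an intention to treat principle". It names a linear mixed-effects model for KCCQ at baseline, 90 and 180 days and credits that model with coping with missing data. It does not state the missing-at-random condition on which this rests.

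The Missing Data Issues part of the same section then adds rules that depend on what is observed:

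- Below 5%, that is, "if the number of observations with missing values is small", the plan says "we will conduct analyses by removing the variables with missing values".
- When more is missing, "we will compare characteristics between dropouts and those who had completed all the study visits".
- Imputation is conditional: "If it is determined that missing data is random, we will resort to methods that impute values". No step follows for the opposite finding.
- If attrition differs significantly by arm, intention-to-treat and as-treated "analyses will be performed to determine the extent to which the missing data may be biasing the results". For the intention-to-treat version, "we will generate actual random raw data values suitable for filling in gaps in an existing database", with five to ten completed data sets analysed and combined.

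The plan does not define as-treated for this purpose. It also promises: "We will also record and report all reasons for dropout and missing data". It expects little missing data, yet the Sample Size and Power Considerations allow for 15% dropout, and section 5 (Randomization and retention) reports that about 90% completed earlier studies.

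**The concern.** Unequal loss between arms is the situation the plan itself singles out, and the tool it assigns cannot answer the question asked of it. An as-treated analysis changes who is compared with whom. The missing scores stay missing, and nothing is assumed about them that was not assumed before. Its distance from the intention-to-treat estimate mainly reflects how attenders differ from non-attenders. The team could be reassured when informative loss has inflated the effect, or alarmed when it has not.

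The conditional imputation rule has a related gap. Comparing dropouts with completers shows whether loss is related to recorded characteristics. It cannot show whether, given those characteristics, loss depends on the unseen score. A patient whose health declined after day 90 and who then stopped responding looks no different in the recorded data from one who stayed well and stopped responding. The plan has no analysis for the case where loss does depend on the unseen score.

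**Working it through.** **Inputs from the plan.** 375 patients randomised 1:1 (187.5 per arm); 15% planned dropout; 158 per arm analysed; KCCQ difference 5; SD 15; two-sided alpha 0.05; past completion about 90%.

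**Assumed inputs, not in the plan.** Loss of 20% in the intervention (SMA) arm and 10% in usual care; non-attendance p = 0.20; a deficit g of 0 to 10 points in non-attenders, counted only in change from baseline because the planned model accounts for baseline; the same observed data in both analyses.

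**1. Plan's own figure.** SE = 15 × √(2/158) = 1.688. Power ≈ Φ(5/1.688 − 1.960) = Φ(1.00) = 0.84, as in Table 2. (375 × 0.85 = 318.75; the plan uses 316.)

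**2. Is the trigger met at 20% versus 10%?** Pooled proportion 0.15; z = 0.10 / √(0.15 × 0.85 × 2/187.5) = 0.10/0.0369 = 2.71, p = 0.007. Yes.

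**3. Informative loss, full attendance.** Observed data predict a 5-point effect, but the missing 20% of SMA patients are 10 points worse than predicted.

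- Truth = 5 − 0.20 × 10 = 3.0.
- Intention to treat = 5.0.
- As-treated = 5.0, because the groups are identical.
- Bias 2.0, gap 0.

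**4. Non-attendance, no informative loss.** Attenders gain 5 points. Would-be non-attenders in either arm do g points worse.

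- Intention to treat = 5 × (1 − 0.20) = 4.0, which is correct.
- The as-treated comparison group pools usual care (0.90 observed, mean −0.20g) with SMA non-attenders (0.20 × 0.80 = 0.16 observed, mean −g). Its mean is −g × (0.90 × 0.20 + 0.16)/(0.90 + 0.16) = −0.321g.
- As-treated = 5 + 0.321g: 5.0 at g = 0 and 8.2 at g = 10.
- Bias 0, gap 1.0 to 4.2.

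The gap is zero where the bias is 2.0, and up to 4.2 where the bias is zero.

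**5. How much informative loss would matter?** Critical difference = t × SE with t ≈ 1.967, the SE held at its available-case value, and an observed difference of 5. Tipping point = (5 − critical difference) / fraction missing. When both arms share the same shortfall, the divisor is the difference in fractions missing.

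| Missing | SE | Critical difference | Shortfall at which significance is lost |
|---|---|---|---|
| 15% per arm, SMA shortfall only | 1.688 | 3.32 | 1.68/0.15 = 11.2 |
| 10% per arm, SMA shortfall only | 1.633 | 3.21 | 1.79/0.10 = 17.9 |
| 20% vs 10%, SMA shortfall only | 1.683 | 3.31 | 1.69/0.20 = 8.4 |
| 20% vs 10%, same shortfall in both arms | 1.683 | 3.31 | 1.69/0.10 = 16.9 |

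A 10-point shortfall in SMA patients alone moves the estimate by 1.0, 1.5 or 2.0 points at 10%, 15% or 20% missing. The KCCQ description in section 8 treats a 10-point change as moderate and a 20-point change as large.

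**6. Reach of the under-5% rule.** Counted by patient, the expected 10–15% loss is above 5%, so the rule does not apply. Counted by assessment (375 × 3 = 1,125), 10% missing day 180 only is 37.5/1,125 = 3.3%, so it applies. At 15% it is 56.25/1,125 = 5.0%, which is not below the limit. If 10% miss both follow-up visits it is 75/1,125 = 6.7%. The plan does not say which count is meant.

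**The case against.** The strongest defence is that the primary analysis is sound and identifiable: an intention-to-treat mixed model, valid under missing at random, with as-treated added to it rather than replacing it. Multiple imputation is compatible with that model, since imputed data can be analysed with it. Monthly calls, telephone visits and mailed surveys should limit loss, and reasons for dropout will be recorded. All of this stands. These measures reduce missingness, but they do not test the assumption about what remains.

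A second defence is that the plan specifies imputation only for the intention-to-treat version. If the as-treated version uses observed scores, the comparison is partly imputed versus observed, and some effect of missingness could show. This is fair: the exact zero in step 3 holds only when both analyses use the same data. But the gap then mixes two things, attendance selection and the effect of imputing, and cannot be read as either.

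Third, a 5-point result withstands sizeable departures, about 8 to 18 points in the cases shown. That also stands. The planned trial is not shown to be fragile, but the plan has no analysis that would demonstrate this robustness.

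On the removal rule, dropping an incomplete covariate would lose no patient. Only if the rule means dropping patients does it discard partial data that the mixed model would use. Step 6 suggests the effect is probably small either way.

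**Conclusion.** The as-treated comparison is not a valid measure of missing-data bias, and the plan has no analysis for loss that depends on unseen scores. The illustrations rest on the assumed 20% versus 10% loss and 20% non-attendance. The 8.2 further requires that non-attenders do 10 points worse in change from baseline, since a deficit already present at baseline would be adjusted away. The tipping points rest on SD 15 and a fixed SE.

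A reader might infer more than this, and the documents do not support it:

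- That the missing-data rules as a whole conflict with the mixed model. They do not; the trouble lies in the as-treated rule, the missing-at-random gate and, on one reading, the removal rule.
- That the comparison would always show no gap. That depends on attendance and on which data each analysis uses.
- That deaths bias the KCCQ result. Deaths by day 180 are expected, and the visible text does not say how they enter the KCCQ analysis. That is an unstated definition, and no bias from it is claimed.

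**What to change.** In Missing Data Issues:

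1. Remove the as-treated analysis as a missing-data check. It may stay as a separately labelled adherence analysis, with as-treated defined.
2. Remove the under-5% rule. State that the Aim 1 mixed model, on all randomised patients with any KCCQ score, is primary whatever the amount or pattern of attrition.
3. Replace the test of whether data are missing at random with one pre-specified delta-adjusted multiple imputation of missing day-180 KCCQ in patients not known to have died. Shifts of 0 to −20 points, varied separately by arm, would be one reasonable choice. Report the tipping point.
4. State how deaths enter the KCCQ analyses, as a clarification.

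The cost is revised wording and one extra analysis on data already collected. No visits or patients are added.
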